6.7 Medical Devices

Blinatumomab must be administered using infusion pumps approved for use by the appropriate regulatory authorities for the country in which the subject is undergoing treatment, in both the inpatient and outpatient setting.

Blinatumomab infusion for solution will be prepared in bags for IV infusion and delivered through infusion lines that are both compatible with the IP as described in the IPIM. The blinatumomab final solution for infusion should not come into contact with the pump at any time.

Additional details for the use of the above mentioned medical devices and specific set of device specifications are provided in the IPIM.

Other non-investigational medical devices may be used in the conduct of this study as part of standard care. These other medical devices, (eg, syringes, sterile needles, alcohol prep pads) that are commercially available are not usually provided or reimbursed by Amgen (except, for example, if required by local regulation). The investigator will be responsible for obtaining supplies of these devices.

6.8 Product Complaints

A product complaint is any written, electronic or oral communication that alleges deficiencies related to the identity, quality, durability, reliability, safety, effectiveness, or performance of a drug(s) or device(s) after it is released for distribution to market or

clinic by either Amgen or by distributors and partners for whom Amgen manufactures the material.

This includes any drug(s), device(s) or combination product(s) provisioned and/or repackaged /modified by Amgen. Drug(s) or device(s) includes IP.

Any product complaint(s) associated with an IP or non-IP(s) or device(s) supplied by Amgen are to be reported according to the instructions provided in the IPIM.

6.9 Excluded Treatments, Medical Devices, and/or Procedures During Screening and Treatment Periods

Subjects are prohibited from receiving the following therapies during the Screening and Treatment Phase of this study:

- Any anti-tumor therapy other than protocol specified therapies:
- Radiation therapy. Note that radiotherapy to previously bulky sites of disease that upon response assessment, **remains** metabolically inactive (Deauville ≤ 4) will not be counted as an event. Intrathecal chemotherapy may be administered if the investigator deems the subject to be at high risk of CNS relapse. Evidence of CNS disease will be reported as relapse or progression.
- Immunotherapy other than blinatumomab
- Chronic systemic (> 7 days) high-dose corticosteroid therapy (dexamethasone > 24 mg/day or equivalent)
- Any other immunosuppressive therapies (except for transient use of corticosteroids for ≤ 7 days)
- Any other investigational agent

Following last response assessment and prior to trial enrollment, subjects are prohibited from receiving additional chemotherapy.

The Exclusion Criteria in [Section 4.1.2](#) describe other medications that are prohibited in this study.

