4.1.1 Inclusion Criteria

101 Subject has provided informed consent prior to initiation of any study-specific activities/procedures OR subject's legally acceptable representative has provided informed consent prior to any study-specific activities/procedures being initiated when the subject has any kind of condition that, in the opinion of the investigator, may compromise the ability of the subject to give written informed consent.

102 Age \geq 18 at the time of informed consent

103 Biopsy proven aggressive B-NHL, including DLBCL NOS, follicular lymphoma Grade 3B, PMBCL, T-cell rich B-cell lymphoma, or DLBCL that represents transformation of indolent NHL, (including follicular, marginal zone, and lymphoplasmacytoid lymphoma excluding chronic lymphocytic leukemia or Hodgkin Lymphoma). Subjects with prior indolent lymphoma must have received therapy after a diagnosis of transformation that is appropriate for aggressive histology as described in 104. The following histologies are not eligible:

- Lymphoblastic lymphoma
- Burkitt lymphoma
- Mantle cell lymphoma

Any histologies not specifically mentioned must be discussed with the medical monitor. For subjects enrolled in the phase 3 portion of study, pathologic samples will be submitted for central confirmation of disease histology.

104 Refractory (no prior CR/CMR) or relapsed (prior CMR) following front line treatment of standard multiagent chemotherapy containing an anthracycline AND an approved anti-CD20 agent. Examples of appropriate therapy include but are not limited to R-CHOP (14 or 21), R-CHOEP, and DA-R-EOCH. For subjects with refractory disease and who have received radiotherapy, PET positivity should be demonstrated no less than 6 weeks after the last dose of radiotherapy

105 Biopsy-proven confirmation of relapsed disease. For subjects with de novo aggressive B-cell lymphoma and primary refractory disease (ie, never achieving CR/CMR), biopsy of persistent disease is preferred but persistent PET positivity (ie, Deauville \geq 4) is acceptable at a minimum. For subjects with transformed disease that has been characterized as refractory, biopsy (core or excisional biopsy) with demonstration of persistent aggressive B-NHL is required

Approved

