5. SUBJECT ENROLLMENT

Before subjects begin participation in any study-specific activities/procedures, Amgen requires a copy of the site's written institutional review board/independent ethics committee (IRB/IEC) approval of the protocol, informed consent form (ICF), and all other subject information and/or recruitment material, if applicable (see [Section 11.2](#)).

The subject or the subject's legally acceptable representative must personally sign and date the IRB/IEC- and Amgen-approved ICF before the commencement of study-specific procedures. Upon completion of the screening period the subject is evaluated by the investigator and providing the subject continues to meet the inclusion/exclusion criteria, the subject is subsequently eligible to be enrolled in the study and either randomized or assigned to a treatment regimen.

For Phase 2, a subject will be considered enrolled into the study when the investigator decides that the subject has met all eligibility criteria and registers enrollment via IVRS.

In Phase 3, a subject will be considered enrolled and randomized into the study when the investigator decides that the subject has met all eligibility criteria and a randomization number is provided via IVRS.

Enrollment will occur after the centralized response assessment to S1 chemotherapy. Subjects with CMR (Deauville \leq 3) will not be enrolled. The investigator is to document this decision and date, in the subject's medical record and in/on the enrollment case report form (CRF).

Each subject who enters into the screening period (defined as the date when the subject signs the IRB/IEC-approved main study ICF) for the study receives a unique subject identification number before any study-related activities/procedures are performed. The subject identification number will be assigned by IVRS. This number will be used to identify the subject throughout the clinical study and must be used on all study documentation related to that subject.

Subjects who fail screening will be allowed to re-screen once.

The subject identification number must remain constant throughout the entire clinical study; it must not be changed after initial assignment, including if a subject is rescreened. This number will not necessarily be the same as the randomization number assigned for the Phase 3 part of this study.

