Appendix D. Response Assessment per the Lugano Classification

5- point scale (Deauville)

1. no uptake above background;
 2. uptake \leq mediastinum;
 3. uptake $>$ mediastinum but \leq liver;
 4. uptake moderately $>$ liver;
 5. uptake markedly higher than liver and/or new lesions;
- X. new areas of uptake unlikely to be related to lymphoma.

Response	Complete Response	Partial Response	Stable Disease	Progressive Disease
PET/CT Response	Complete Metabolic Response	Partial Metabolic Response	No Metabolic Response	Progressive Metabolic Disease
Target Masses	Score 1, 2, or 3 with or without a residual mass	Score 4 or 5 reduced uptake compared with baseline residual mass(es) of any size	Score 4 or 5 no significant change in FDG uptake from baseline	Score 4 or 5 with an increase in intensity of uptake from baseline and/or new FDG-avid foci consistent with lymphoma
New Lesions	None	None	None	New FDG-avid foci consistent with lymphoma rather than another etiology
Bone Marrow	No FDG avid focal lesions	Residual uptake higher than uptake in normal marrow but reduced compared with baseline	No change from baseline	New or recurrent FDG-avid foci

Approved

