This study is event-driven and will conclude when approximately 236 death events in phase 3 have occurred. It is anticipated that the enrollment period will be approximately

Approved

33 months, and the study duration will be approximately 52 months from the date that the first subject is enrolled, randomized (approximately 12 months from the completion of randomization in phase 3).

At the end of phase 2, when all phase 2 subjects have had an opportunity to have a tumor assessment by week 12, a data analysis will be done to facilitate the decision whether to proceed to phase 3. If the study will not continue for the phase 3 portion, the study will conclude when phase 2 subjects have had an opportunity to complete long term follow-up.

If the study only includes the phase 2 portion, the enrollment period is approximately 12 months, and the study duration will be approximately 24 months from the date the last subject completes treatment.

[Section 6.9 Excluded Treatments, Medical Devices, and/or Procedures During Screening and Treatment Periods](#), bullet 2

Replace:

- Radiation therapy. Note that radiotherapy to previously bulky sites of disease that upon response assessment is metabolically inactive ($\text{Deauville} \leq 4$) will not be counted as an event. Intrathecal chemotherapy may be administered if the investigator deems the subject to be at high risk of CNS relapse. Evidence of CNS disease will be reported as relapse or progression.

With:

- Radiation therapy. Note that radiotherapy to previously bulky sites of disease that upon response assessment, **remains** metabolically inactive ($\text{Deauville} \leq 4$) will not be counted as an event. Intrathecal chemotherapy may be administered if the investigator deems the subject to be at high risk of CNS relapse. Evidence of CNS disease will be reported as relapse or progression.

[Section: 7.2.4 Safety Follow-up Visit\(s\)](#), paragraph 1

Add:

For phase 2 and phase 3, all subjects, including subjects who withdraw from treatment early, will complete a safety follow-up visit approximately 30 (± 3) days after their last dose of blinatumomab or 30 (± 3) days **or** after the last day of the last cycle of IC chemotherapy. In the event that a planned cycle of therapy is delayed beyond 30 days, then the safety follow-up may be delayed without a protocol deviation. However, in the event that therapy is not resumed, the subject should be seen for safety follow-up as

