6.2 Efficacy Endpoints

Response rate will be based on the central review of radiographic assessment of PET-CT scans using the Lugano Classification. DOR, DOCR, PFS and HSCT related endpoints will be based on investigator's review of radiographic assessment of PET-CT scans using the Lugano Classification and clinical assessment.

100 Day non-relapse mortality (NRM) Rate after HSCT

Non-relapse mortality rate at 100 days after HSCT will be estimated using the cumulative incidence function with relapse or deaths due to relapse treated as competing risks. Only subjects who achieve a response **per investigator's review** and undergo autoHSCT are included. Only deaths without relapse are considered as events.

Allogeneic HSCT (alloHSCT) Rate

Allogeneic HSCT rate is the proportion of responder **per investigator's review** (subjects who achieved either CMR or PMR during the treatment) who have undergone alloHSCT **while in remission and without any other anti-cancer treatment**.

Autologous HSCT (autoHSCT) Rate

Autologous HSCT rate is the proportion of responder **per investigator's review** (subjects who achieved either CMR or PMR during the treatment) who have undergone autoHSCT **while in remission and without any other anti-cancer treatment**

Complete Metabolic Response (CMR)

CMR is determined by the central review of radiographic assessment of PET-CT scans using the Lugano Classification. Subject's CMR status is determined by whether the subject achieves CMR during the first 12 weeks of treatment since starting blinatumomab.

Complete Metabolic Response Rate (CMR Rate)

Complete metabolic response rate (CRR) is the proportion of subjects who have achieved CMR by the central review of radiographic assessment of PET-CT using Lugano Classification among all subjects in the respective analysis set.

Duration of Response (DOR)

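### Protocol Section 6.9 calls a site with Deauville score 4 metabolically inactive, against Section 5, inclusion 105 and Appendix D; the cut-off should be 3

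*Protocol*

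**What the plan says.** Protocol Section 6.9 lists what subjects may not receive during screening and treatment. The list opens with "Any anti-tumor therapy other than protocol specified therapies", and radiation comes next. A note under radiation makes an exception: radiotherapy to a previously bulky site that is, at response assessment, "metabolically inactive (Deauville ≤ 4) will not be counted as an event".

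Elsewhere the protocol uses the Deauville scale as follows.

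- Section 5, on response to first salvage: "Subjects with CMR (Deauville \leq 3) will not be enrolled".
- Section 4.1.1, inclusion 105, on primary refractory disease: "persistent PET positivity (ie, Deauville \geq 4) is acceptable at a minimum".
- Appendix D, CMR column: "Score 1, 2, or 3 with or without a residual mass".
- Appendix D, partial metabolic response (PMR) column: "Score 4 or 5 reduced uptake compared with baseline residual mass(es) of any size". The columns for no metabolic response (NMR) and progressive metabolic disease (PMD) also require score 4 or 5.

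Appendix D describes score 4 as uptake moderately higher than liver.

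Amendment 2 touched this very sentence of Section 6.9. The replaced text read "upon response assessment is metabolically inactive" and the current text has a different verb. The cut-off is 4 in both.

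SAP Section 6.2 states that "DOR, DOCR, PFS and HSCT related endpoints will be based on" the investigator's review. For the transplant rates, the two transplant analysis sets and the mobilization rate, SAP Sections 6.2, 7.1, 7.2 and 10.5.2 require remission and no other anti-cancer or anti-tumor therapy. These definitions do not mention radiotherapy.

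**The concern.** Consolidating a formerly bulky site that has gone cold on PET is different from irradiating a site that still takes up tracer above liver. The first can reasonably be disregarded when judging the assigned drug. The second treats residual active disease by other means. Section 6.9 intends to disregard only the first, since it speaks of inactive sites, but its cut-off also admits score 4.

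The affected subjects fall within the analysed population. A PMR can carry score 4, and PMR responders are in the denominator of the transplant rates. If the 6.9 note were used to decide what counts as other therapy, a responder irradiated at a score 4 site could be kept in a transplant or mobilization result from which the SAP condition would remove that subject.

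**Working it through.** The plan gives no figure to reproduce here, and no sample size, power or error rate is involved. The check sets the cut-offs side by side, then traces where the 6.9 note could act.

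**Step 1: cut-offs by score**

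| Place | Scores 1–3 | Score 4 | Score 5 |
|---|---|---|---|
| Section 6.9 | inactive | inactive | not inactive |
| Section 5 | CMR | less than CMR | less than CMR |
| Inclusion 105 | not PET-positive | PET-positive | PET-positive |
| Appendix D | CMR | PMR, NMR or PMD | PMR, NMR or PMD |

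Score 4 is the only score on which the rows disagree, and Section 6.9 is the only row out of line. Inclusion 105 calls score 4 positive in words; Section 5 and Appendix D do so by leaving it out of CMR. The settings differ (Section 5 concerns response to first salvage, inclusion 105 front-line refractory disease), but Section 7.3.11 makes Appendix D the standard for treatment response, which is the assessment that the 6.9 note relies on. With a cut-off of 3 in Section 6.9, all four rows agree.

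**Step 2: results the note cannot reach**

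- *12-week CMR* (SAP 4.1.1): central reading of PET/CT. The definition contains no radiotherapy rule.
- *PFS* (Protocol 10.1.1.2, SAP 6.2): progression or death.
- *Duration of response* (same sections): relapse or progression, or death. The sensitivity analysis censors at transplant, not at radiotherapy.

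Radiotherapy is neither an event nor a censoring reason in any of these, so changing 4 to 3 changes none of them.

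**Step 3: results it could reach**

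What remains are the results conditioned on no other therapy: the transplant rates, the autologous and allogeneic transplant analysis sets, the 100-day non-relapse mortality computed on those sets (SAP 10.5.2), and the mobilization rate. Read plainly, the SAP condition removes an irradiated subject whatever the Deauville score. The note would matter only if someone carried it over into that condition, and neither document says to do so.

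**Step 4: size**

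The documents do not say how many subjects might have a score 4 site irradiated before transplant or mobilization. The number may be zero, so no shift in a rate is calculated.

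**The case against.** The strongest reply is that the clause does little. Section 6.9 prohibits radiation in the period it covers; the Deauville wording is a counting note and does not tell sites when to irradiate. No efficacy definition has a radiotherapy event for it to discount. Not being counted as an event is also different from not being anti-cancer treatment, so the SAP condition can be applied without consulting 6.9. Finally, SAP Section 10.5.2 plans sensitivity analyses on the full analysis set for the transplant rate (autologous or allogeneic) and for mobilization. Neither carries the no-other-therapy condition, so neither depends on how radiotherapy is classified.

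All of this stands as a limit on the consequences. The sensitivity analyses do not extend to the 100-day mortality result, but that leaves only a possible effect on one secondary estimate. None of it removes the contradiction: the sentence is current protocol text, it states a threshold, and the threshold disagrees with the protocol's own response criteria.

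A reader might infer two stronger things. One is that the primary result, PFS or duration of response is biased; Step 2 shows that their definitions do not use the clause. The other is that the SAP must state which radiotherapy counts, by site score, with an added eCRF field to support it. The documents do not require that. The SAP wording already covers any irradiated subject. A rule admitting irradiated sites with scores 1 to 3 would loosen that condition and would leave non-bulky sites undefined.

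**Conclusion.** Wrong as written, and minor. Section 6.9 classes Deauville 4 as inactive, while Section 5, inclusion 105 and Appendix D place it outside CMR or call it positive. Confidence in the mismatch is high, because it rests only on comparing current protocol text.

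No effect on any endpoint has been shown. A possible effect is confined to secondary results that are only estimated, with confidence intervals or cumulative incidence, in a single-arm phase 2. It would arise only if the 6.9 note were used to interpret the SAP's no-other-therapy condition.

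**What to change.** In Protocol Section 6.9, change the cut-off in the radiotherapy note from Deauville ≤ 4 to Deauville ≤ 3. The cost is one character. Section 12.1 requires IRB/IEC approval for every amendment, so the edit can wait for the next one and does not justify an amendment of its own. The SAP definitions and the eCRF can stay as they are.

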4.1.2 Exclusion Criteria

- 201 CMR following S1 chemotherapy
- 202 Treatment within 30 days prior to randomization with another investigational device or drug study (ies). Other investigational procedures while participating in this study are excluded
- 203 Prior anti-CD19-directed therapies
- 204 Prior HDT with autologous HSCT
- 205 Prior allogeneic HSCT
- 206 Presence of clinically relevant central nervous system (CNS) pathology such as epilepsy, paresis, aphasia, stroke, severe brain injury, dementia, Parkinson's disease, cerebellar disease, organic brain syndrome, or psychosis
- 207 Evidence of CNS involvement by NHL

- 208 Known infection with human immunodeficiency virus or chronic infection with hepatitis B virus (hepatitis B surface antigen positive) or hepatitis C virus (anti-hepatitis C virus positive)
- 209 History of malignancy other than B-NHL within the past 3 years with the exception of:
- Malignancy treated with curative intent and with no known active disease present for ≥ 3 years before enrollment and felt to be at low risk for recurrence by the treating physician
 - Adequately treated non-melanoma skin cancer or lentigo maligna without evidence of disease
 - Adequately treated cervical carcinoma in situ without evidence of disease
 - Adequately treated breast ductal carcinoma in situ without evidence of disease
 - Prostatic intraepithelial neoplasia without evidence of prostate cancer
 - Adequately treated urothelial papillary noninvasive carcinoma or carcinoma in situ
- 210 Subject has known sensitivity to immunoglobulins or any of the products or components to be administered during dosing.
- 211 Subject likely to not be available to complete all protocol-required study visits or procedures, and/or to comply with all required study procedures to the best of the subject and investigator's knowledge.
- 212 History or evidence of any other clinically significant disorder, condition or disease (with the exception of those outlined above) that, in the opinion of the investigator or Amgen physician, if consulted, would pose a risk to subject safety or interfere with the study evaluation, procedures or completion.

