Neurologic Events	3	
 • Interrupt blinatumomab until the event improves to grade ≤ 1 and administer corticosteroids (refer to Table 3) • Restart no less than 72 hours after the initial observation of the grade 3 event at the following dose levels: 
 ○ If event occurred at 112 $\mu\text{g}/\text{day}$, resume at 28 $\mu\text{g}/\text{day}$ ○ If event occurred at 28 $\mu\text{g}/\text{day}$, resume at 9 $\mu\text{g}/\text{day}$ • Escalate up 1 dose level after 7 days if toxicity does not reoccur. Increase dose stepwise at 7-day intervals to target dose of 112 $\mu\text{g}/\text{day}$ if toxicity does not reoccur. • Permanently discontinue if: 
 ○ Initial grade 3 neurologic event occurred at 9 $\mu\text{g}/\text{day}$, ○ Initial grade 3 neurologic event does not improve to grade ≤ 1 within 7 days, OR ○ Grade 3 neurologic event reoccurs at the lower dose level within 7 days of re-initiation
	4	
 • Permanently discontinue blinatumomab
	4	
 • Permanently discontinue blinatumomab

Approved

ALP=alkaline phosphatase; ALT=alanine aminotransferase; AST=aspartate aminotransferase; CRS=cytokine release syndrome; INR=international normalized ratio; MRI=magnetic resonance imaging; RUQ=right upper quadrant; TBL=total bilirubin; ULN=upper limit of normal
 * Obtain brain MRI and perform cerebro spinal fluid (CSF) analysis, if there are no contraindications

Table 2. Infusion Interruption/Dose Modifications of Blinatumomab due to Adverse Events

Toxicity	Grade	Instructions for Treatment Interruption and Restart
Seizure*		
 Interrupt blinatumomab, administer corticosteroids (refer to Table 3) and antiseizure medication per local practice For restart, refer to grade 3 neurologic events above for dose level rules for re-instituting infusion Do not re-initiate blinatumomab until 7 days after the last seizure and after therapeutic levels of antiseizure medication are likely to have been achieved Permanently discontinue if a second seizure occurs with re-initiation of blinatumomab at any dose

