7.3.13 Radiographic Assessment

PET/CT scans with whole body images, from base of skull to mid-thigh, will be conducted. Examinations should be consistent across all timepoints including: the amount of tracer, location of injection, arm location, and scan delay.

The following data should be collected per center: standard procedures, height, weight, gender, administered dose, time between dose administration and imaging, blood glucose level, number of cycles of S1 chemotherapy, and time between blood glucose level sampling and tracer injection. Additionally, the number of cycles of chemotherapy and date and the use of G-CSF/GM-CSF (dose and dates administered) should also be provided.

PET images should be converted to standardized uptake values maps to support comparison across timepoints and to standardize viewing conditions CT anatomical coverage: chest, abdomen, and pelvis (and neck if not visualized with chest).

If PET and CT are acquired on the same day, it is strongly recommended that PET is performed prior to the CT with IV contrast. Refer to the imaging manual for additional details, including requirements for submission of pre-S1 scans.

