10. STATISTICAL CONSIDERATIONS

10.1 Study Endpoints, Analysis Sets, and Covariates

10.1.1 Study Endpoints

10.1.1.1 Primary Endpoint

Phase 2 and Phase 3:

- CMR as determined by central radiographic assessment of PET/CT scans using the Lugano Classification

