4.1 Study Endpoints

4.1.1 Primary Endpoint

- CMR: CMR is determined by central radiographic assessment of PET-CT scans **ie, central review** using the Lugano Classification. Subject's CMR status is determined by whether the subject achieves CMR during the first **12 weeks** after initiation of blinatumomab.

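### Protocol 6.9 treats CNS disease as relapse or progression, but CMR and OR rest only on a central PET-CT read from skull base to mid-thigh, with no rule for CNS lymphoma documented by CSF or MRI

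*Protocol*

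**What the plan says.** - **Reporting rule.** Protocol 6.9, in the bullet on radiotherapy and intrathecal chemotherapy: "Evidence of CNS disease will be reported as relapse or progression". It makes no exception for a clean body scan and names no endpoint.
- **Entry.** Exclusion criterion 207 (Protocol 4.1.2) rules out "Evidence of CNS involvement by NHL".
- **Primary endpoint.** Protocol 10.1.1.1: "CMR as determined by central radiographic assessment of PET/CT scans using the Lugano Classification". SAP 6.2: "CMR is determined by the central review of radiographic assessment of PET-CT scans using the Lugano Classification". SAP 4.1.1 and 10.5.1 also take CMR from central review in the first 12 weeks, and SAP 6.2 defines OR from the same read.
- **Scan field.** Protocol 7.3.13: "PET/CT scans with whole body images, from base of skull to mid-thigh, will be conducted".
- **Other sources of CNS findings.** Table 6 asks for CSF analysis after a grade 3 or higher neurologic event or a seizure, and Table 10 lists CSF flow cytometry as a local test. A Table 2 footnote marked on the seizure row reads: "Obtain brain MRI and perform cerebro spinal fluid (CSF) analysis, if there are no contraindications".
- **DOR and PFS.** The opening of SAP 6.2, and SAP Section 11, base these on investigator review of PET-CT together with clinical assessment. The individual DOR and PFS definitions in SAP 6.2 are narrower. They use clinical progression from the CRF only when there is no radiographic assessment in long-term follow-up.

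**The concern.** The protocol can give the same subject two statuses. CSF or MRI may document lymphoma in the CNS while the PET-CT from skull base to mid-thigh is negative. Section 6.9 then makes the subject a relapse or progression, while the CMR definition makes the same subject a complete responder. Nothing in either document says which takes precedence.

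The primary endpoint of a 36-subject single-arm phase is at stake. For CMR and OR the error runs one way: a missed CNS finding can add a responder but cannot remove one. Protocol 10.2.1 says that rejecting a 15% rate would support moving to phase 3, so the CMR count carries a decision as well as an estimate.

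**Working it through.** **1. Does any existing rule already make this subject a non-responder?**

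| Rule | Where | Covers the case? |
|---|---|---|
| Additional chemotherapy before the response assessment scores as non-response | Protocol 6.2.1; not repeated in the SAP | Only if chemotherapy was given before the scan. CNS disease that is untreated, treated after the scan, or treated by other means is not covered. Whether the intrathecal chemotherapy allowed in 6.9 counts is not stated. |
| No post-baseline disease assessment means no CMR | SAP 9.3 | No; this subject has a scan. |
| CMR requires no new lesions | Protocol Appendix D | In principle it excludes new disease, but progression there is described by FDG uptake, and neither document says that a CSF or MRI finding enters the read. |

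The remaining case is intracranial or CSF-only lymphoma, documented on or before the response assessment, with a clean body PET-CT and no additional chemotherapy before the scan. FDG-avid spinal disease within the scanned field is already visible to the reader. CNS disease arising after a valid CMR is a relapse and does not undo the CMR.

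Table 5 lists no brain imaging or CSF at screening. CNS lymphoma found on study is therefore newly documented, but not necessarily newly arisen.

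**2. The plan's own figure (Protocol 10.2.1; SAP 3.2).** Inputs: n = 36, null 15%, alternative 40%, one-sided alpha 0.025, stated power 90%.

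P(X ≥ r) = Σ C(36, x) p^x (1 − p)^(36 − x), summed over x = r to 36.

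- p = 0.15: P(X ≥ 10) = 0.0351; P(X ≥ 11) = 0.0137. The smallest count that rejects is 11.
- p = 0.40: P(X ≥ 11) = 0.910. The stated 90% reproduces.

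**3. What one subject is worth.** 1/36 = 2.8 percentage points.

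| CMRs | Rate | Exact 95% CI | One-sided p against 15% |
|---|---|---|---|
| 10/36 | 27.8% | 14.2% to 45.2% | 0.0351 |
| 11/36 | 30.6% | 16.35% to 48.1% | 0.0137 |

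One subject therefore decides whether the reported interval excludes 15%, but only if the count falls exactly there.

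**4. Sensitivity to an assumed rate.** The documents give no rate of CNS lymphoma. Assume that a share m of all subjects is scored CMR despite documented CNS lymphoma and that the true CMR rate is 15%. Then P(X ≥ 11) is computed at p = 0.15 + m:

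| m (assumed) | Expected extra CMRs, 36m | P(X ≥ 11) |
|---|---|---|
| 0 | 0 | 0.0137 |
| 1% | 0.36 | 0.0216 |
| 2% | 0.72 | 0.0325 |
| 3% | 1.08 | 0.0470 |
| 5% | 1.80 | 0.0889 |

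The nominal 0.025 is passed between m = 1% and m = 2%. This shows how little slack there is. It does not show that such a rate will occur.

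**The case against.** The sentence in 6.9 sits in a list of excluded treatments and can be read as an instruction on event reporting, not a response criterion. CMR is by design a central metabolic read. Appendix D allows no new lesions in a CMR, and a subject given chemotherapy for CNS disease before the scan is already a non-responder. CNS involvement is excluded at entry. The sensitivity of 10 against 11 of 36 holds for any misclassification, and SAP Sections 5 and 10.5.1 plan an estimate with an exact interval; the test appears only in the sample-size section.

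All of this stands as a limit on size. It does not settle which status applies to the remaining subject.

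Three stronger readings are tempting but not supported:

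- **The central reader cannot see CSF or MRI results.** Protocol 7.3.13 defers details to an imaging manual that is not among the documents. What can be said is that neither the protocol nor the SAP gives a rule.
- **DOR and PFS ignore CNS disease.** SAP 6.2 and Section 11 include clinical assessment for these endpoints. The fault is the narrower sentence in the individual definitions.
- **The 22% grade 3 neurologic event rate in Protocol 2.2 indicates how many subjects are affected.** It counts adverse events on blinatumomab, not CNS lymphoma. The brain MRI footnote is also marked on the seizure row only, so MRI is not shown to follow every grade 3 neurologic event.

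**Conclusion.** The gap is real and narrow. Followed to the letter, the plan can score a subject as CMR and OR while Section 6.9 calls the same subject relapsed or progressed. Each such subject adds 2.8 percentage points to the CMR rate, always upward.

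The expected effect is small. No rate is given; as an assumption, 0 to 2 of 36 subjects would mean 0 to 5.6 points (2/36). A reader might infer that the phase 2 result is likely to be wrong, or that every CNS event invalidates a CMR. The documents support neither. The conclusion rests on the text of the protocol and SAP, and an imaging manual with an explicit rule could narrow it. A rule that decides the primary endpoint should still be stated in the SAP.

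**What to change.** 1. In SAP 4.1.1 and 6.2 (CMR and OR) and Protocol 10.1.1.1, add: a subject with CNS lymphoma documented by CSF, MRI or biopsy on or before the response assessment is not a CMR or OR, whatever the body PET-CT shows. CNS disease arising after a valid CMR remains a relapse.
2. In the SAP 6.2 definitions of DOR and PFS, reconcile the sentence restricting clinical progression to follow-up without imaging with the clinical assessment named at the start of SAP 6.2 and in Section 11. Documented CNS lymphoma should count as progression even when a body PET-CT exists.
3. Name the data source for the derivation. CSF is a local, event-triggered test, and the documents describe no response form for brain MRI or CNS biopsy.

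Cost: some wording, one derivation and a check that the finding is captured. In rare cases a locally documented result, obtained only in subjects who were worked up, would override the central read in an open-label trial. Reporting how many subjects were overridden makes that visible. The CMR rate may be slightly lower; the sample size does not change.
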